## 1.5 Why Iodophor Skin Preparations May Reduce Open Fracture SSI

The only surgical skin preparation effectiveness data available for open fracture management come from the FLOW trial. Secondary multivariable analyses of 2,447 patients with open fractures found that when compared to chlorhexidine solutions, iodophor-based skin antiseptic preparation solutions could be protective against complications (Adjusted Hazard Ratio 0.88, 95% CI: 0.69–1.12). However, the wide CI suggests iodophor solutions may reduce the odds of infection by as much as 31% or increase it by as much as 12%, leaving its superiority as a fracture care surgical preparation solution unresolved.

There are several chemical properties to suggest povidone-iodine may be more effective than CHG at preventing open fracture SSI. Firstly, povidone-iodine has a broader spectrum of antimicrobial activity. Secondly, many open fracture patients require repeat surgical debridement and therefore, these patients will receive multiple exposures to the pre-operative antiseptic solution. Extended use of povidone-iodine has not been associated with the selection of resistant bacterial strains, whereas bacterial resistance to chlorhexidine has been documented. He methods for detecting CHG resistance are challenging and its clinical significance remains uncertain, these early observations heighten interest in establishing the comparative effectiveness of iodophors versus CHG.

## 1.6 Why Iodophor Skin Preparations May Reduce Open Fracture Reoperations

While the primary rationale for using antiseptic skin preparation solutions is to reduce the risk of SSI, many fracture healing complications are associated with indolent infections. These low-grade infections typically do not exhibit clinical signs consistent with SSI. Instead, they present several months post-fracture fixation and are only detected from deep tissue samples collected during secondary surgeries to treat fractures that fail to heal (nonunion). Previous fracture non-union studies have identified an infectious etiology in 31–38% of cases.  Similarly, results from the FLOW trial suggest that 58% of the reoperation events were caused by fracture nonunion or a hardware failure related to infection, wound-healing problem, or bone-healing problem (n= 188/323). In addition, among a series of 211 patients requiring reoperation for deep post-operative fracture infections, 40% of open fracture infections occurred beyond the 90-day surveillance period for SSI.  Therefore, given the rationale that povidone-iodine may be more effective in

preventing SSI, it is clinically plausible that its use may also reduce unplanned open fracture reoperations.

## 1.7 Lack of Surgeon Consensus

The FLOW trial demonstrated a clear divide among orthopaedic surgeons regarding their choice to use the two most common antiseptic solutions during open fracture fixation surgery. Iodophor solutions were used in 54% of the surgeries performed, while 41% were performed using chlorhexidine solutions. The remaining surgeons either used both iodophor and chlorhexidine (4%), or alcohol with no iodophor or chlorhexidine (1%). Building upon the lack of consensus among orthopaedic surgeons participating in the FLOW trial, our research team conducted an internet-based survey and several interviews with orthopaedic surgeons to understand the reasons for the lack of consensus in the use of surgical preparation solutions. Similar to the observations of the FLOW trial, there was nearly an equal split between the use of iodophor and chlorhexidine solutions. More insight was gained in interviews with the surgeons. Three main drivers for surgeon decision-making were identified: 1) they continued to use the antiseptic solution shown to them during their surgical training, 2) they used the solution recommended by their hospital, or 3) they felt the tissue toxicity was less with their chosen solution. No surgeon could cite a clinical study that helped guide their decision, despite all surgeons indicating they believed the antiseptic solution was important for reducing their patient's risk of SSI. Limited consensus among surgeons reflects a lack of compelling evidence on the optimal approaches to surgical skin preparation, further vindicating the need for a large definitive trial.

The Aqueous-PREP trial, A Pragmatic Randomized trial Evaluating Pre-operative aqueous antiseptic skin solutions in open fractures, will address these gaps in the literature.

#### 2.0 STUDY OBJECTIVES AND HYPOTHESES

#### 2.1 Study Objectives and Hypotheses

The overarching objective of this trial is to compare the effectiveness of an aqueous pre-operative antiseptic skin preparation with 10% povidone-iodine versus 4% CHG for the management of open fractures. A ranked order for assessing effectiveness will be used, with *surgical site infection (SSI)* as the primary comparison (primary objective) and *unplanned fracture-related reoperations* as the secondary comparison (secondary objective). While previous randomized controlled trials in general surgery and gynecology demonstrated superior efficacy of chlorhexidine-alcohol solutions to reduce SSIs, results from larger populations of general surgery patients and the recently completed FLOW trial suggest iodophor-based solutions could be more effective than chlorhexidine in open fracture patients. Therefore, we hypothesize that aqueous solutions of 10% povidone-iodine will be more effective than aqueous 4% CHG to reduce 90-day SSIs or unplanned fracture-related reoperations within one year of injury.

#### 2.2 Subgroup Objectives

The Aqueous-PREP trial will also explore the possibility of differential treatment effects of the pre-operative antiseptic skin solutions among clinically important open fracture subgroups. Subgroups will be defined by: i) the severity of open fracture (Gustilo-Anderson type I or II versus III); ii) upper extremity versus lower extremity open fractures; and iii) severity of wound contamination. High-grade soft tissue injury (Gustilo-Anderson type III), lower extremity open

fractures, and moderate/severe wound contamination are established predictors of SSI and reoperations from the FLOW trial.  In addition, there are known differences in patients' skin flora based on anatomic region of injury. As a result, it is likely that the study interventions may be more effective in certain subgroups. Due to its broader spectrum of antimicrobial activity, the increased effectiveness observed by Swenson *et al.*, and the possible benefits observed in the FLOW trial, we hypothesize that 10% povidone-iodine antiseptic skin solution will be associated with a larger reduction in odds for SSI and reoperation in open fracture patients with worse fracture severity, lower extremity fractures, and more severely contaminated wounds.

#### 3.0 TRIAL DESIGN

#### 3.1 Summary

This study is a multi-center pragmatic cluster randomized crossover trial of a minimum of 1,540 participants with open extremity fractures requiring surgical management. The unit of randomization is the orthopaedic practices within clinical sites (clusters), with individual patients being the unit of analysis. Recruitment for each treatment group will be performed in multiple iterations of approximately two-month periods. Each orthopaedic practice will initially be randomized to use one of two pre-operative aqueous surgical skin preparation solutions (10% povidone-iodine or 4% CHG) for open fracture surgeries at their institution (Figure 1). Upon completion of the two-month period, each orthopaedic practice will crossover to the alternative treatment allocation and complete another two-month recruitment period. This process of alternating treatment periods (crossovers) will continue until the minimum sample size is achieved and the study's budgeted recruitment duration is completed. Upon completion of recruitment, it is expected that each orthopaedic practice will enroll a minimum of 77 patients per treatment, and that most clinical sites will exceed this minimum recruitment goal. Clinical site personnel will screen potential patients for eligibility, and if eligible, they will be invited to participate in the trial. Study participants will be assessed at regular intervals in the one year following their fracture. The primary outcome will include any SSI event from the time of open fracture to the end of the 30and 90-day post-operative periods from their definitive fracture management surgery. The secondary outcome will include unplanned fracture-related reoperations that occur within one-year of their fracture. A blinded Adjudication Committee will review SSIs and unplanned fracturerelated reoperations to confirm that they meet the criteria for being a study event.

[figure not shown]

Figure 1: Randomized Treatment Allocation, Cluster Crossover, and Recruitment

#### 3.2 Pragmatic-Explanatory Continuum

In accordance with recommended methodology standards, we have used the PRagmatic-Explanatory Continuum Indicator Summary (PRECIS-2) toolkit to evaluate the Aqueous-PREP trial design decisions to determine whether these decisions will lead to a study that answers, "Does this intervention work under usual conditions?" (pragmatic) versus "Can this intervention work

under ideal conditions?" (explanatory). The PRECIS-2 tool uses a 5-point Likert scale in 9 domains to evaluate the continuum of design choices. A domain score of 5 indicates "very pragmatic," while a score of 1 suggests "very explanatory." **Table 1** outlines the investigators' assessment of the trial design and the rationale for each assessed score and **Figure 2** displays the PRECIS-2 wheel.

**Table 1: PRECIS-2 Score** 

Domain	Score	Rationale	
Eligibility	5	Eligibility criteria are very broad and include all fracture patients that would be treated in all hospital environments.	
Recruitment	5	Recruitment of all consenting fracture patients treated at each participating hospital will be performed.	
Setting	4	Recruitment is occurring at multiple sites across the US and Canada; however, since most of the recruiting hospitals are regional referral centers the setting is "mostly pragmatic."	
Organization	The interventions do not need an increase in providers or care delive compared to the usual antiseptic care provided. For each antiseptic solution brief in-service training session will be provided to the clinical sites, as per mew product/procedure that is being introduced into an operating room.		
Flexibility (delivery)	5	The interventions will be delivered in the usual care manner with no advice on allowed co-interventions or strict protocols to ensure compliance.	
Flexibility (adherence)	-	This section is left blank according to PRECIS-2 guidance because the intervention is provided prior to patient consent and individual patient compliance is not an issue. If provider adherence is considered, the study design is rather pragmatic (4) because there will be limited encouragement to follow the manufacturer's directions for use, other than periodic newsletters, investigator meetings, and possible provider survey during the recruitment period.	
Follow-up	5	All study follow-up is consistent with usual care.	
Primary outcome	5	The outcome has been validated by patients as being very relevant to the study participants and it does not require specialized expertise beyond the treating physician for diagnosis.	
Primary analysis	5	All available study data will be used for analysis following the intention to treat principle.	

[figure not shown]

Figure 2: PRECIS-2 Wheel

#### 4.0 METHODS

## 4.1 Study Setting, Cluster Eligibility, and Selection of Clusters

This study will be coordinated by the Methods Center at the Center for Evidence-Based Orthopaedics (CEO), McMaster University, Hamilton, Ontario and by the Administrative Center within the Department of Orthopaedics at the University of Maryland School of Medicine, R Adams Cowley Shock Trauma Center, Baltimore, Maryland. Patients will be enrolled from at least 12 clinical sites. Clusters (orthopaedic practices within clinical sites) will be carefully screened prior to participation in the Aqueous-PREP study. Clinical site inclusion criteria are: 1) adequate research personnel infrastructure to manage the study; 2) adequate open fracture volume to complete enrollment within the study timeline (i.e., a minimum of 77 open fractures per year); 3) commitment from all or most orthopaedic surgeons to participate in the trial; and 4) ability to use the two aqueous-based preparation solutions. The exclusion criteria are: 1) lack of interest in the trial; 2) anticipated challenges with complying with the protocol; 3) conflicting studies, in the judgment of the Principal Investigators, that would inhibit patient participation; and 4) budgeting or contract constraints.

The screening process will begin with potential clinical sites completing a feasibility questionnaire that asks about research experience and infrastructure, open fracture volume, current practice patterns, and interest in participating in the trial. Clinical sites that meet the eligibility criteria at this stage will be invited to participate in a series of teleconferences to review study and clinical logistics in detail with members of the study team. The Principal Investigators and study personnel

will further vet the clinical sites during these calls and will ask about hospital and patient demographics to ensure that a variety of fracture patient populations and referral patterns, ranging from large urban trauma centers to rural community hospitals, are included in the Aqueous-PREP study. Study personnel will document reasons for clinical site ineligibility. Upon selection, clinical sites will be asked to complete a questionnaire that will detail current surgeon preferences and practices for pre-operative surgical preparation techniques and co-interventions known to influence the incidence of SSIs (see Section 4.7).

## 4.2 Eligibility Criteria

Broad eligibility criteria will be used to increase the generalizability of the trial.

#### The inclusion criteria are:

- 1. Patients 18 years of age or older.
- 2. Open fracture of the appendicular skeleton.
- 3. Received or will receive definitive fracture treatment with a surgical implant(s) (e.g., internal fixation, external fixation, joint prosthesis, etc.).
- 4. Open fracture wound management that includes formal surgical debridement within 72 hours of their injury.
- 5. Will have all planned fracture care surgeries performed by a participating surgeon or delegate.
- 6. Informed consent obtained.
- 7. Patient enrolled within 3 weeks of their fracture.

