#### The exclusion criteria are:

- 1. Patients that did not or will not receive the allocated pre-operative surgical preparation solution due to a medical contraindication.
- 2. Received previous surgical debridement or management of their open fracture at a non-participating hospital or clinic.
- 3. Open fracture managed outside of the participating orthopaedic service (e.g., hand fracture managed by plastic surgeon).
- 4. Chronic or acute infection at or near the fracture site at the time of initial fracture surgery.
- 5. Burns at the fracture site.
- 6. Incarceration.
- 7. Expected injury survival of less than 90 days.
- 8. Terminal illness with expected survival less than 90 days.
- 9. Previous enrollment in a PREP-IT trial.
- 10. Currently enrolled in a study that does not permit co-enrollment.
- 11. Unable to obtain informed consent due to language barriers.
- 12. Likely problems, in the judgment of study personnel, with maintaining follow-up with the patient.
- 13. Excluded due to sampling strategy.

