## 4.3 Recruitment Strategy

## 4.3.1 Patient Screening and Consent

Patients 18 years of age or older who present to a recruiting hospital for treatment of an open fracture will be screened for participation within 3 weeks of their fracture. To screen patients presenting with an open fracture(s) for eligibility, designated study personnel at each clinical site will develop a patient enrollment plan. This plan will typically consist of daily participation in orthopaedic patient rounds and a review of daily listings of hospital admissions for patients with open fractures. Upon identification, the study personnel will screen the patient for eligibility and if eligible, approach them for informed consent. Study participants must be enrolled within 3 weeks of their fracture(s) and enrollment may take place at any time within this window. If the patient is unable to provide informed consent (e.g., due to their injury) at the time they were initially identified, informed consent may be delayed until they are able to provide informed consent. Alternatively, if the patient is unable to provide informed consent, informed consent may be obtained from their proxy, with consent obtained from the patient when/if the patient is able to provide consent. Allowing informed consent from a patient's proxy healthcare decision maker will reduce the risk of recruitment bias against the most severely injured patients. In addition, potentially eligible patients will be approached to participate in the trial, even if they did not receive the correct pre-operative antiseptic skin solution. This is consistent with the intention-to-treat principle (ITT) and is necessary to maintain the prognostic balance achieved during the cluster randomization. All screened patients will be classified as included, excluded, or missed. See Table 2 below for the Schedule of Events.

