## 4.5 Blinding

The orthopaedic team (including the study coordinators) cannot be blinded to the treatment allocation as the antiseptic solutions are visually distinguishable and these individuals need to lead the implementation of the cluster-crossover protocol at their clinical site. The Adjudication Committee Members and data analysts will be blinded to the study treatment. All interpretation of study results will initially be done in a blinded manner by developing two interpretations of the results. One interpretation will assume treatment A is povidone-iodine, the other interpretation will assume it is CHG. Once the data interpretations for each assumption are finalized, the data will be unblinded and the correct interpretation will be accepted.

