## 4.8 Outcome Measures

#### 4.8.1 Primary Outcome

The primary outcome is SSI, guided by the CDC's National Healthcare Safety Network reporting criteria (2017), which includes superficial incisional SSI within 30 days and deep incisional or organ/space SSI within 90 days of fracture surgery (**Table 3**). Since the management of some open fractures may have more than one operative procedure as part of an intentionally staged surgical plan (e.g., multiple irrigation and debridements, wound closures, temporary stabilization surgeries, definitive fixation surgery), the primary outcome will include any SSI event from the date of open fracture to the end of the 30- and 90-day post-operative surveillance periods from their definitive

fracture management surgery. For participants with multiple open fracture regions, the date of the definitive fracture management surgery will be matched to the open fracture region with the SSI.

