The consent process will typically take place in the patient's hospital room or in the outpatient fracture clinic, either before or after the patient has had surgery(ies) to manage their open fracture. If the patient is unable to provide informed consent (e.g., due to their injury, language restrictions) within 3 weeks of their fracture, informed consent will be obtained from their proxy. In addition, if a patient has been discharged from hospital prior to being invited to participate in the study, a delegated member of the clinical care team may obtain their consent by telephone, as approved by the IRB of Record.

To obtain informed consent, delegated study personnel should follow the below procedures:

- Present study information in a manner that is understandable to the potential participant/proxy.
- Discuss the study with the potential participant/proxy and answer any questions he or she asks.
- Allow the potential participant/proxy an opportunity to discuss participation with their family, friends, or family physician, if desired.
- Confirm that the participant/proxy understands the risks and benefits of participating in the study and that their participation is voluntary.
- Complete and obtain signatures for informed consent form and obtain contact information from the participant/proxy.
- Provide /send the participant/proxy with a paper/electronic copy of the signed consent form

Consent may be obtained electronically or using pen and paper consent forms, as approved by the IRB of Record.

The process of obtaining and documenting informed consent will be completed in accordance with local Good Clinical Practice recommendations. Consent procedures and forms, and the communication, transmission and storage of patient data will comply with the IRB of Record and Department of Defense requirements for compliance with The Health Insurance Portability and Accountability Act.

Upon providing informed consent, study participants will be followed for 12 months from their fracture. Given the short follow-up time, the need for a regular reassessment of consent will not apply; however, participants may withdraw their consent at any time.

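### Eligibility can be decided up to 21 days after fracture, after a primary event may have occurred, by unblinded staff using criteria not tied to earlier facts; the selection this allows is neither prevented nor tested.

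*Combined protocol and SAP*

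**What the plan says.** All references are to the combined protocol, which contains the statistical plan as section 5.0.

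- **Timing of entry.** Section 4.3.1: "Study participants must be enrolled within 3 weeks of their fracture(s) and enrollment may take place at any time within this window". Section 7.2 places consent "either before or after the patient has had surgery(ies) to manage their open fracture".
- **Start of the outcome window.** Section 4.8.1: "the primary outcome will include any SSI event from the date of open fracture". Table 2 collects SSI and reoperation data at the enrolment visit itself.
- **Who decides.** Section 4.3.1 on screening: "This plan will typically consist of daily participation in orthopaedic patient rounds". Section 4.5: "The orthopaedic team (including the study coordinators) cannot be blinded to the treatment allocation".
- **Criteria not fixed in time (section 4.2).** Inclusion 3: "Received or will receive definitive fracture treatment with a surgical implant(s". Exclusion 12: "Likely problems, in the judgment of study personnel, with maintaining follow-up with the patient". Inclusion 5 also looks forward: "Will have all planned fracture care surgeries performed by a participating surgeon or delegate".
- **A criterion that is fixed in time.** Exclusion 4 removes a patient for infection only if it was present when the first fracture surgery took place.
- **Checks.** Screened patients are sorted into included, excluded or missed (4.3.1), and a flow diagram is planned (5.2.1). Section 5.2.4 lists six sensitivity analyses. None concerns events dated before consent, and no text asks for screening results by solution.

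**The concern.** Allocation is by cluster and period, so a patient's solution is known before that patient is screened. The solution acts at the first surgery, yet the decision to enter the patient may come up to three weeks later. By then a primary event may have happened, and the person judging eligibility may know both the event and the solution.

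Exclusion 12 is the wider route. It is a free judgement about future follow-up, and nothing confines it to facts that predate the wound's course. Section 4.6.5 allows a site to be withdrawn if primary-outcome follow-up falls below 95%, which gives staff a reason to use it.

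Inclusion 3 is a narrower route. Suppose a limb in temporary fixation becomes infected and is amputated before definitive fixation. A patient consented before the amputation was still expected to receive an implant. A patient first assessed afterwards neither received one nor will. The same course counts as an event in one case and leaves the trial in the other.

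If such omissions differed by solution, the SSI and reoperation comparisons would be biased. Analysis by allocated group cannot repair this, because it covers only those enrolled. Blinded adjudication sees only enrolled patients' events.

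**Working it through.** **1. The plan's own figures (section 5.1, Table 5).** Baseline SSI risk is 12.5% and the risk ratio 0.65, so the povidone-iodine risk is 0.125 × 0.65 = 8.125%. The odds ratio is (0.08125/0.91875)/(0.125/0.875) = 0.619, matching the tabulated 0.62. The ICC is 0.095/(0.095 + π²/3) = 0.028, as stated. 1,400 × 1.10 = 1,540. Simulating 10 clusters, 2 periods and between-cluster variance 0.095, with a pooled logistic model and cluster sandwich errors, gives 79.7% power at 1,400 and 83.2% at 1,540. The plan's figures are therefore reproduced. The simpler two-proportion test used below gives 76.8% at 700 per arm. Expected events are 700 × 0.125 = 87.5 and 700 × 0.08125 = 56.9.

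**2. The figure that is missing.** Section 1.4 says nearly half of the infection complications in the earlier open-fracture irrigation trial were identified between 30 and 90 days. It does not give the share by day 21, still less the share known before consent. All inputs in steps 3 and 4 are assumptions.

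**3. Differential omission, no true effect.** Assume 20–40% of SSIs are known before consent, and that enrolment of those patients differs between arms by 10–20%.

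- Shift in risk: 12.5 × 0.20 × 0.10 = 0.25 point, up to 12.5 × 0.40 × 0.20 = 1.0 point. This is 6–23% of the planned difference of 12.5 − 8.125 = 4.375 points.
- Events lost from one arm of 700: 700 × 0.0025 = 1.75, up to 700 × 0.010 = 7.
- Apparent risk ratio: 12.25/12.5 = 0.98, down to 11.5/12.5 = 0.92. The lower figure is 0.93 if these patients also leave the denominator: (80.5/693)/0.125.

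With k events removed from numerator and denominator of one arm, the two-sided test at 5% gives:

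| k | Apparent risk ratio | Type I error |
|---|---|---|
| 2 | 0.98 | 5.2% |
| 4 | 0.96 | 5.9% |
| 7 | 0.93 | 8.0% |
| 9 | 0.91 | 10.1% |

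Wider assumptions give larger effects. The range starts at zero, since the difference between solutions may be nil.

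**4. Equal omission.** If a fraction f of events is lost in both arms, the odds in each arm become p(1 − f)/(1 − p). The factor (1 − f) cancels, so the odds ratio stays at 0.619. With early shares of 10–40% and half of those patients omitted (f = 0.05 to 0.20), the risk ratio is 0.649 to 0.644. Power falls from 76.8% to between 75% and 69%, holding 700 per arm. This assumes the early share of events is the same under both solutions.

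**The case against.** The strongest reply is that the text shows no mechanism that differs by solution. Neither inclusion 3 nor exclusion 12 mentions the solution, and the same staff enrol under both, alternating about every two months. This stands. A reader might infer that the plan biases the comparison between arms; the documents support only an opportunity for that.

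A reader might also infer that early severe infections routinely disappear through inclusion 3. The documents do not support this. Screening is normally daily, it is consent rather than identification that is described as delayed, and external fixation qualifies when it is the definitive treatment. The route needs a limb that ends without any definitive implant and a late first assessment.

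Safeguards exist. Exclusion 4 does not reach infections arising after the first surgery. Proxy consent is adopted to keep the most severely injured in the trial. Patients given the wrong solution are still approached. Late consent was discussed with ethics board members and patient advisors. The screening classes, flow diagram and adjustment for prognostic imbalance are indirect checks, so it would be too strong to say that nothing planned could hint at a problem. None of them, however, ties exclusion 12 or inclusion 3 to earlier facts, compares screening by solution, or examines events dated before consent.

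Finally, judging inclusion 3 by a plan recorded at first debridement would be more than a wording change. Section 4.8.4 describes no such record, and the population and outcome window would change. That is right, and the fix below does not require it.

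**Conclusion.** The concern holds as an unguarded opportunity for selection. Each link is in the text: entry to day 21, outcome counted from fracture, unblinded screeners, and two criteria not tied to earlier facts although exclusion 4 is. Bias in the SSI or reoperation comparison requires omission that differs by solution, which the documents neither show nor rule out. Equal omission leaves the odds ratio alone and costs some power.

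No size can be fixed. On the assumed inputs, about 2 to 7 events lost from one arm of 700 move a null risk ratio to about 0.98 to 0.92, with type I error of 5.2–8.0%. About 9 lost events roughly double it, to 10.1%. One or two lost events hardly matter. The case for acting is that the repair is cheap and makes an otherwise largely hidden selection checkable.

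**What to change.** 1. **Section 4.2.** Limit exclusion 12 to circumstances present at admission or before the first debridement, with the reason logged. State that an infection, reoperation or amputation after the first debridement does not by itself make a patient ineligible under inclusion 3.
2. **Reporting (5.2.1 or the separate analysis plan).** Give by solution the numbers included, excluded (by reason) and missed, the days from fracture to consent, and the number of participants whose SSI or reoperation preceded consent.
3. **Section 5.2.4.** Add a sensitivity analysis of the primary and secondary outcomes restricted to participants event-free at consent.

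The third item removes differential inclusion of early events, but it cannot recover patients who were never enrolled. It also conditions on what happened after treatment, so it is a check beside the main analysis and not a replacement for it. The by-solution table in item 2 is the only part that looks at patients left out.

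Cost: slightly more logging and analysis, a few participants who never receive a definitive implant (for whom the start of the 30- and 90-day windows must be stated), and lower precision in the sensitivity analysis. The planned sample size does not change.
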